- Importance of robust referral mechanisms to mental health services.
- Monitoring of participants expectations from their involvement in the study (e.g. expecting this to affect their legal status). Moreover, members of the research team will clearly reaffirm that the participation in this study will not provide refugees with any benefits in terms of housing, resettlement or relocation procedures.
- Safety of members of the research team involved in the study, including, if required, gender matching and awareness of socio-demographic differences to participants and impact this may have on the research encounter.
- Intervention delivery: importance of gender matching.
- Facilitator training and supervision to ensure their competency to practice and protect against burnout / additional stress due to being exposed to participants experiences.

The participation in the study will be on a voluntary basis. During the informed consent procedures for screening and for the study this will be explicitly stated in written (in the informed consent form) and with oral communication by the interviewer.

An international EAB will supervise all the ethical issues related to the trial. Activities of the EAB are described in detail in a Memorandum of Understanding (Appendix 2). The EAB will help the consortium keep high ethical standards, which will ultimately enhance the quality of research, increase its likely social impact, promote integrity and a better alignment of RE-DEFINE with social needs and expectations. The EAB will make sure that relevant steps are undertaken to minimize risks or provide solutions in case relevant psychological problems are detected during screening or during the course of the study. The EAB will indirectly supervise three main aspects: (1) recruitment, inclusion and exclusion criteria, and informed consent procedures; (2) data management (protection and privacy); (3) vulnerability of the population.

Benefits and risks *Potential benefits*

• Access to a new preventive psychosocial intervention, and receiving the intervention for free;

- Regular and careful attention to the psychological status during the study. Assessments from members of the research team will guarantee close monitoring of participants mental health:
- Benefits in terms of psychological symptoms and functioning, quality of relationships, and solutions of specific problems both related and unrelated to their traumatic experiences, breaking of unhealthy patterns, and a significant reduction in feelings of distress.
- Contributing to a research that may limit the incidence of newly diagnosed psychiatric disorders in refugees resettled in Turkey.

Potential risks

- There are no guarantees of what participants will experience, and of the duration of changes. For example, it could be that benefits won't last for long periods;
- Based on data from randomized controlled trials already testing the SH+ we are not expecting the intervention worsening mental health condition of participants. However, it could be that participants will experience a transient increase of their mental health problems. In order to mitigate these risks, follow-up assessments and networking with NGOs have been planned to closely monitor the psychological status of participants. In addition facilitators will be trained in basic helping skills and identification of serious adverse events (e.g. imminent risk of suicide) which will further aid identification of any adverse reactions to SH+. Facilitators will be regularly supervised by mental health professionals to further address this risk;
- Participants will not be able to choose in which study arm they will be allocated;
- Participants might experience uncomfortable feelings like sadness, guilt, anger, frustration, and loneliness. Approaching feelings that participants have tried to avoid for a short or long period of time may be painful;
- The participant burden related to the involvement in this study may compete with ongoing responsibilities faced by newly re-settled people (i.e., housing, language issues, new medical system, etc.). This issue has been considered when planning study timeline and assessments. The study is pragmatic and participation implies only 4 assessments of 1 hour each. However, it will be taken into careful consideration throughout the course of the study;
- Participants might feel uncomfortable in a group setting.

INFORMED CONSENT FORMS

Three informed consent forms specific to Turkey have been prepared and attached:

- 1) one for screening (for the pilot or trial phase) (Appendix 3)
- 2) one for participation in the trial phase RCT (Appendix 4)
- 3) one for participation in the pilot (Appendix 5, with differences from Appendix 4 highlighted in green).

BUDGET

The budget has been uploaded (see Appendix 10).

This study has received funding by the European Union Horizon 2020 Research and Innovation Action (RIA), under grant agreement n. 779255. A budget table detailing study related costs have been produced agreed and signed by the involved sites in a Grant Agreement.

COLLABORATION WITH OTHER SCIENTISTS OR RESEARCH INSTITUTIONS

The scientists collaborating in this project are all listed in the General Information section of this document and Appendix 1.

LINKS TO OTHER PROJECTS

This project is related to current WHO project trialing a related low-intensity intervention, including: *Problem Management Plus (PM+)*, where trials have been completed in Kenya and Pakistan (WHO Ethical Research Committee Protocol IDs: RPC627; RPC656; RPC705), Self Help Plus (SH+) in Uganda (RPC758) and Step by Step (ERC.0002797)

CURRICULUM VITAE OF INVESTIGATORS

These are attached.

OTHER RESEARCH ACTIVITIES OF THE INVESTIGATORS

Other research activities by the investigators are summarised in the attached CVs.

FINANCING AND INSURANCE

The implementing agency will ensure free of charge follow-up on any adverse events, or serious adverse events, caused by the study. Therefore, insurance is not deemed necessary.

LIST OF APPENDICES

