Arabic speaking people including Syrians under the temporary protection of Republic of Turkey and other Arabic speaking immigrants and asylum seekers who screen positive at the General Health Questionnaire (≥ 3) and without a formal diagnosis of any psychiatric disorders according to the M.I.N.I. International Neuropsychiatric Interview (M.I.N.I.) will enter the study. After random allocation they will receive the 5-session SH+ or the ETAU. Assessments will be performed by masked members of the research team immediately after intervention, at 6 months (primary outcome), and a 12 months after randomization.

Time frame

The recruitment phase will last 12 months. After the screening, eligible participants will be assessed at baseline before randomization, immediately post-intervention, and at 6- and 12-monthsfollow-up. The SH+ intervention delivery will be conducted in around 5 weeks (1 session per week).

Expected outcomes

The expected outcomes are a reduction in the incidence of psychiatric diagnoses at 6-month follow-up, and a general improvement in mental health symptoms, psychological functioning, well-being, and economic outcomes at each assessment, in refugees in the SH+ intervention arm, as compared to ETAU.

GENERAL INFORMATION

Project title:

RE-DEFINE: Refugee Emergency – DEFining and Implementing Novel Evidence-based psychosocial interventions

Name of the sponsor/funder:

European Commission, H2020-SC1-2016-2017, topic: SC1-HCO-07-2017, project ID: 779255. The study sponsor has no role in study design; collection, management, analysis, and interpretation of data; writing of the report; and the decision to submit the report for publication. The study sponsor had no ultimate authority over any of the listed activities.

Name and title of the investigators:

[name], PhD

Coordinator

World Health Organization (WHO)

Department of Mental Health and Substance Abuse

[name]

[name] Email: [contact] [contact]

Responsibility: Responsible Officer within WHO for the study

[name], DClinPsy

Technical Officer

World Health Organization (WHO)

Department of Mental Health and Substance Abuse

[name]

[name] SEP

Email: [contact] [contact]

Responsibility: WHO focal point for the study

[name]

Professor of Psychiatry,

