The member of the research team will have no responsibility in checking that refugees actually follow the suggested clinical pathway. Psychiatric care costs will be covered in accordance with the local healthcare system. Given the limited services and transient nature of some refugees in Turkey, it will not be possible for the research team to always check if Syrian refugees actually follow the suggested clinical pathway. Local healthcare systems will cover psychiatric care costs. An SOP will define in detail how the referral to mental health care services will be conducted.

Trial phase *Pilot phase*

Before starting the study we will conduct a preliminary pilot phase with 3-4 participants for each site. This phase will allow testing different aspects related to the delivery of the intervention and assessments, feasibility, and time, prior to the performance of the trial. Participants of the pilot study will not be included in the final sample size. However, they will receive the experimental condition, and a close monitoring of their psychological status through two psychological assessments (one at baseline, and one at the end of the intervention). These assessments will be composed of the same instruments that will be used in the fully-powered trial.

Trial phase assessment

Assessments will take place at screening, at baseline (before random allocation), post-intervention (0-1 week after intervention), and at 6- and 12- months after randomization. The assessments at 6- and 12- months will be performed in person or by telephone/videoconferencing, to ensure the required rates of follow up. Telephone or online assessment and counselling has been used in a range of studies, with a critical review concluding that findings to date are positive and online counselling can have a similar impact and replicate the therapeutic conditions found in face-to-face encounters¹. In addition, a previous study has shown that a mixture of online and telephone based assessments for inclusion in a remote writing based intervention for Post Traumatic Stress Disorder (PTSD) can be feasibly implemented with war traumatised individuals in Iraq². This approach is continuing to be used widely (http://ilajnafsy.bzfo.de/portal/en/)

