Together, these findings suggest that remote therapy and thus assessment can be safely and feasibly applied. The use of audio/video communication will be piloted and used should the pilot show that this can be done safely and feasibly. For the Turkey site, audio/video assessments may be used for both screening and assessments).

Methods of assessment will be recorded, and if necessary, accounted for in the analyses. See Appendix 8 for copies of all screening and outcome measures.

Version 4.1 11 March 2019 12

-

¹ Richards, D. and Viganó, N. (2013), Online Counseling: A Narrative and Critical Review of the Literature. J. Clin. Psychol., 69: 994–1011. doi:10.1002/jclp.21974

² Knaevelsrud C, Brand J, Lange A, Ruwaard J, Wagner B. Web-Based Psychotherapy for Posttraumatic Stress Disorder in War-Traumatized Arab Patients: Randomized Controlled Trial J Med Internet Res 2015;17(3):e71

At baseline, socio-demographic data including sex, age, country of origin, education, religion, marital status and work status will be collected using an ad-hoc form developed specifically for RE-DEFINE. The form will also collect information on education, housing, employment opportunities in Turkey (as measures to improve social integration). Information on the adverse life events and environmental stressors will be collected using the Harvard Trauma Questionnaire Part A (HTQ) (30) and the Post-Migration Living Difficulties (PMLD) and the Recovery Environment (31). We will administer the HTQ Part A (30), in which respondents are asked whether they have experienced each of the events, and a 17-item Checklist for Post-Migration Living Difficulties (PMLD) (31).

In addition, the following assessment scales will be administered (as reported in Table 1 below and Appendix 7 assessment schedule):

- 1. baseline: ad-hoc recruitment form, WHODAS 2.0, PHQ-9, WHO-5 Wellbeing index, PSYCHLOPS, HTQ Part A, PCL-5, EQ-5D-3L, and CSSRI-EU (adapted);
- 2. post-intervention: GHQ-12, M.I.N.I., WHODAS 2.0, PHQ-9, WHO-5 Wellbeing index, PSYCHLOPS, PMLD, and PCL-5;
- 3. 6-month follow-up: GHQ-12, M.I.N.I., WHODAS 2.0, PHQ-9, WHO-5 Wellbeing index, PSYCHLOPS, PMLD, PCL-5, EQ-5D-3L, and CSSRI-EU (adapted);
- 4. 12-month follow up: GHQ-12, M.I.N.I., WHODAS 2.0, PHQ-9, WHO-5 Wellbeing index, PSYCHLOPS, PMLD, PCL-5, EQ-5D-3L, and CSSRI-EU (adapted).

Table 1 Overview of measures that will be administered during the study

Concept	Screening	Baseline	Post- intervention	6-month follow-up	12-month follow-up

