- GHQ-12 post-intervention, at 6- and 12-months follow-up;
- Proportion of participants with a psychiatric diagnosis (M.I.N.I.) post-intervention and at 12 months of follow-up;
- WHODAS 2.0 post-intervention, at 6- and 12-months follow-up;
- PHQ-9 post-intervention, at 6 and 12 months of follow-up;
- WHO-5 Wellbeing index post-intervention, at 6 and 12 months of follow-up;
- PSYCHLOPS post-intervention, at 6 and 12 months of follow-up;
- EQ-5D-3L: at 6 and 12 months of follow-up;
- PCL-5 post-intervention, at 6 and 12 months of follow-up;
- CSSRI-EU (adapted) at 6 and 12 months of follow-up;
- Proportion of participants leaving the study early (dropouts).

Proportion of participants with a psychiatric diagnosis (M.I.N.I.) post-intervention and at 12 months of follow-up

The proportion of participants with a diagnosis of any mental disorder post-intervention and at 12-months of follow-up will be compared between the two groups through the chi-square test. A multivariate analysis will be performed through a Poisson regression model, with a robust error variance, to estimate relative risks directly and to explore the potential confounding effect of prognostic factors, and the interactions with treatment (57).

GHQ-12, WHODAS 2.0, PHQ-9, WHO-5 Wellbeing index, PSYCHLOPS, PCL-5 post-intervention, at 6- and 12- months of follow-up

For each questionnaire, in case of missing items, the Corrected Item Mean Substitution method (58), will be used (i.e. the item mean across participants weighted by the subject's mean of completed items), using information from subjects belonging to the same treatment arm for the same follow-up time.

The hypothesis that the experimental intervention has no effect on GHQ-12, WHODAS 2.0, PHQ-9, WHO-5 Wellbeing index, PSYCHLOPS, PCL-5 scores will be tested by performing seemingly unrelated regression (59), for each follow-up, controlling for baseline values. In case of joint statistical significance of the coefficients related to treatment status, the effect of treatment on each score will be evaluated through appropriate statistical methods for repeated measurements.

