Comprehensive use of annual health and social care resources will be assessed by means of completing the adapted CSSRI-EU at baseline and at 6-month follow-up. Information on the unit-costs of the used services will be gained by the cost compilation for the UK health and social care system (Curtis & Burns, 2017). For services not listed in the UK compilation, price lists, fee charges, reimbursement claims and other sources will be used to identify unit costs. Costs of informal services provided by relatives or volunteers will be estimated on the basis of average salaries per hour. Total direct costs of service use will be calculated by multiplying service units with unit costs. Six months costs from the two surveys will be added to annual costs. Productivity losses will be estimated for asylum seekers and refugees with work permissions by means of the human capital approach (Brouwer & Koopmanschap, 1998) on the basis of group-specific average salaries. All costs will be calculated in 2017 UK £.

Total costs of health and social care use including costs of the SH+ implementation will be investigated with regard to the cost driving effects of asylum seekers and refugees characteristics and the impact of different levels of coverage, different macroeconomic, social and health care indicators by estimating regression based cost functions (Knapp, 1998).

Incremental cost-effectiveness ratios (ICER) will be calculated for the additional costs of gaining one quality-adjusted life year (QALY) by implementing SH+ compared to standard care. QALYs will be estimated on the basis of EQ-5D-3L using country specific utility scores (Szende, Janssen, & Cabases, 2014). The stochastic uncertainty of the ICER will be estimated by nonparametric bootstrapping with 2000 replications. Maximum willingness to pay necessary for a 95 % probability of the SH+ intervention to be cost-effective at a MWTP range between UK£ 0 and 50,000 will be estimated by means of the cost-effectiveness acceptability curve based on the net-monetary-benefit approach (Glick, 2010). Net-monetary benefit (NMB) for each participant will be computed as the QALY gain per patient (QALY) multiplied by the maximum willingness to pay (MWTP) for one QALY minus the direct or

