total costs (C) per patient (NMB_i = QALY_i*MWTP-C_i) for a MWTP range between UK£ 0 and 50,000 in increments of UK£ 5,000 (Hoch et al., 2002). Incremental NMB will be computed by regressing the NMB on study group (Hoch, Briggs, & Willan, 2002). Results of ICEA will be interpreted according to UK MWTP thresholds recommended by the NICE (Appleby, 2016) and alternatively by country specific thresholds provided by (Woods, Revill, Sculpher, & Claxton, 2016).

Interim analyses

No interim analysis is planned for this trial.

Individual Participant Data meta-analysis

Anonymized Individual Participant Data (IPD) from this study will be re-analysed in an IPD meta-analysis collecting IPD from all available trials on SH+. An ad-hoc protocol for the IPD meta-analysis will be developed.

This secondary analysis of data (IPD meta-analysis) will be mentioned in the informed consent form for participants.

QUALITY ASSURANCE

Participants in the study may directly benefit from their participation in the SH+ intervention, which is based on AMBT techniques that are empirically supported. Their participation will furthermore inform adaptation of the SH+ manual into multiple languages, and thus improve knowledge about delivering mental health interventions in the study areas. Since SH+ is non-pharmacological and there is a broad evidence base for its use, it is unlikely that adverse effects due to the intervention will occur. Adverse events will be responded to as described above. The EAB will play a key role in monitoring adherence to the trial protocol and ensuring research quality as well as prompt and accurate reporting of adverse events.

EXPECTED OUTCOMES OF THE STUDY

The expected outcomes are a reduction in the incidence of psychiatric diagnoses at 6-month follow-up, and a general improvement in mental health symptoms, psychological functioning, well-being, and economic outcomes at each assessment, in refugees in the SH+ intervention arm, as compared to ETAU.

DISSEMINATION OF RESULTS AND PUBLICATION POLICY

A detailed dissemination and communication plan will be developed by WHO in collaboration with project partners. The plan will be circulated across the study sites for comments and final approval.

Local Community

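### EQ-5D-3L, the only source of QALYs, is not taken at the post-intervention visit, so utility over the first 6 months must be interpolated, with an error of unknown direction and size

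*Protocol*

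**What the plan says.** The visit list under Trial phase assessment gives, for the second contact, "post-intervention: GHQ-12, M.I.N.I., WHODAS 2.0, PHQ-9, WHO-5 Wellbeing index, PSYCHLOPS, PMLD, and PCL-5". EQ-5D-3L is in the lists for baseline, 6 months and 12 months. Table 1 shows the same pattern, and Analysis of the secondary outcomes has "EQ-5D-3L: at 6 and 12 months of follow-up". The three places agree, so the omission is deliberate or at least consistent.

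The assessments are timed as "post-intervention (0-1 week after intervention), and at 6- and 12- months after randomization", and the Time frame paragraph of the Project Summary puts delivery of SH+ at around 5 weeks.

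Under Cost-effectiveness analysis (CSSRI), "QALYs will be estimated on the basis of EQ-5D-3L using country specific utility scores". No other utility source is named. These QALYs feed the ICER, the acceptability curve and the net monetary benefit, the last two over a willingness to pay of £0 to £50,000. The section states neither how utilities are joined between visits nor the period over which QALYs accrue.

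The Project Summary and the section Expected outcomes of the study both anticipate "a general improvement in mental health symptoms, psychological functioning, well-being, and economic outcomes at each assessment". Under Potential risks the protocol allows that "it could be that benefits won't last for long periods", and that some participants could have a passing increase in mental health problems.

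**The concern.** Cost-effectiveness is part of the trial's stated objective, and its effect measure is an area under a utility curve. That curve has no observed point between its start and month 6, although everyone is interviewed in between. WHODAS 2.0, PHQ-9, WHO-5, PSYCHLOPS and PCL-5 are taken at baseline and at all three later visits; utility is not.

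A gain that appears after the course and has gone by month 6 would count as nothing, and so would a temporary worsening. If the utility effect is still present at month 6, the QALY difference depends on an assumption about the path that the trial cannot check with utility data. An analysis plan can choose an interpolation rule, but it cannot supply utilities that were never collected. The protocol also expects economic improvement at every assessment, while the post-intervention visit carries neither economic instrument (EQ-5D-3L or CSSRI-EU).

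**Working it through.** The protocol states no QALY, utility or cost-effectiveness figure, so there is none to reproduce. The check is how far the QALY difference over months 0 to 6 moves when a post-intervention point is added.

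**From the protocol:** EQ-5D-3L at baseline, 6 and 12 months; a course of about 5 weeks with the visit 0 to 1 week later; upper willingness to pay £50,000.

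**Assumed, because the protocol does not give them:** straight lines between observed points; no utility difference between arms at baseline; visit at week 6, so t = 6/52 = 0.115 year; between-arm utility difference d at that visit and D at month 6 (0.5 year).

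**Formulas**

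- With the extra point: 0.5 × t × d + 0.5 × (d + D) × (0.5 − t) = 0.25d + 0.192D
- On the planned schedule: 0.5 × 0.5 × D = 0.25D
- Amount missed: 0.25d − 0.058D (in general 0.25d − 0.5tD)

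The amount missed is zero when d = (0.058/0.25)D, about 0.23D. Above that the planned schedule understates; below it, it overstates.

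**Results, months 0 to 6 (rounded at the last step)**

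| d | D | With week-6 point | Planned schedule | Missed | Value at £50,000 |
|---|---|---|---|---|---|
| 0.05 | 0 | 0.0125 | 0 | 0.0125 | £625 |
| 0.05 | 0.025 | 0.0173 | 0.0063 | 0.0111 | £553 |
| 0.05 | 0.05 | 0.0221 | 0.0125 | 0.0096 | £481 |
| 0.0115 | 0.05 | 0.0125 | 0.0125 | 0 | £0 |
| 0 | 0.05 | 0.0096 | 0.0125 | −0.0029 | −£144 |

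The first three rows capture 0%, 36% and 57% of the 6-month gain; the last overstates it by 30%.

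**Over 12 months.** For a constant gain of 0.05 from week 6 to month 12, months 6 to 12 add 0.5 × 0.05 = 0.025 to both totals: 0.0471 with the extra point and 0.0375 without. The ratio is 0.0375/0.0471, about 80% captured. The absolute error stays at 0.0096.

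**Sensitivity**

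- For d from 0.02 to 0.08, with D between 0 and d, the missed amount runs from 0.0038 (d = D = 0.02) to 0.020 (d = 0.08, D = 0), or £192 to £1,000 at £50,000.
- At £25,000 all values halve; the understated cases at d = 0.05 become about £240 to £313.
- With the visit at week 8, the case d = D = 0.05 falls from 0.0096 to 0.0087. The fully faded case stays at 0.0125, because with D = 0 the timing drops out.

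**The case against.** The EQ-5D-3L schedule is internally consistent. The two economic instruments are placed together at the same three visits, and the outcome is secondary. The primary analysis is untouched.

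Three stronger readings are tempting and are not supported.

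- **That the plan draws a straight line from baseline to month 6.** No interpolation rule is given, and an analysis plan may well hold one. It could also use PHQ-9, WHODAS 2.0 or PCL-5, which are taken post-intervention, to inform the path. That stands, but such a path would be modelled and not observed.
- **That the effect should be largest just after the course, so that QALYs are biased against SH+.** The protocol does not say so. The trial enrols people without a disorder and tests prevention of diagnoses at 6 months. Such an effect could build up over time, and the last row of the table shows that the sign then reverses.
- **That the protocol expects benefit to fade or participants to worsen.** Potential risks names both only as possibilities and says that worsening is not expected. Fading between months 6 and 12 would be seen, because EQ-5D-3L is taken at both.

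The size also needs care. The value d = 0.05 has no source in the protocol, the percentages for months 0 to 6 shrink over 12 months, and £50,000 is the ceiling of the range. Groups of 10 to 40 must form before delivery, so the visit may fall later than week 6. All of this stands and is reflected in the ranges shown.

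Burden is the remaining argument: the protocol names it as a risk and limits participation to four assessments of one hour. It does not defeat the change. The 6-month visit carries the same eight instruments plus EQ-5D-3L and the CSSRI of about 20 minutes under the same limit.

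**Conclusion.** The gap is real, and analysis cannot fill it with observed utilities: none are collected between baseline and month 6, and QALYs have no other source. Its direction and size are unknown. Under the stated assumptions, a utility difference of 0.05 at the visit means an understatement of 0.0096 to 0.0125 QALY per participant, about £480 to £625 at the top of the willingness-to-pay range. A late-building effect of 0.05 means an overstatement of about 0.003. There is no error when the early difference is about 0.23 of the month-6 difference. If QALYs run to 12 months, a constant sustained gain is still about 80% captured.

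This is a cheap improvement to a secondary economic outcome. It is not an error in a stated figure, and the documents do not show that the cost-effectiveness result will be biased in a particular direction.

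**What to change.** Add EQ-5D-3L to the post-intervention assessment in both arms. Amend the visit list under Trial phase assessment, Table 1, the list under Analysis of the secondary outcomes, and Appendix 7. State under Cost-effectiveness analysis that QALYs are the area under the utility curve over baseline, post-intervention, 6 and 12 months, using each participant's actual assessment dates.

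The cost is a schedule amendment and a few more minutes with a two-page questionnaire at a visit that already takes place, within the stated hour. No new visit or staff is needed.

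If the schedule cannot change, state the interpolation rule, add sensitivity analyses on the month 0 to 6 utility path that include an early and a late effect, and limit the expectation of economic improvement to the visits where economic instruments are used.
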